7.1.2 Study Intervention Restart or Rechallenge after Stopping Criteria Met

Patients who require treatment interruption > 28 days for a related AE will be withdrawn from the study.

Patients who require a dose reduction after recovery from the AE causing a treatment interruption should be seen in clinic. At the Investigator's discretion, restarting a patient's study treatment at the modified dose prior to a clinic visit using the patient's previous study treatment supply is allowed. However, the rationale and instructions for how the patient should modify their daily dose of study treatment should be documented.

After a dose reduction, if treatment is tolerated at the reduced dose for ≥ 14 days, a dose increase to the original dose is allowed (i.e., rechallenge). Patients should be seen in clinic and receive a new supply of study treatment reflecting the modified dose. Rechallenge without a clinic visit is not allowed, unless discussed with the Medical Monitor. Recurrence of the same AE after a rechallenge should follow the dose interruption/modification steps outlined above. However, in these cases if the AE recurred within 4 weeks of the rechallenge, a subsequent dose increase is not allowed.

A new Grade 3 or higher AE occurring while the patient is receiving a reduced dose should require treatment discontinuation. Discussion with the Global Medical Monitor is required before restarting treatment.

Treatment discontinuation may be required if the AE causing the dose interruption and dose reduction re-occurs at Grade 2 or higher while the patient is receiving the reduced dose. Discussion with the Global Medical Monitor is required before restarting treatment.

7.2 Treatment Discontinuation/ Withdrawal from the Study

7.2.1 Treatment Discontinuation

Treatment discontinuation is defined as any patient who permanently stops receiving study drug. A patient should be discontinued from study treatment if, in the opinion of the Investigator or Sponsor, it is medically necessary, or if it is the wish of the patient.

Patients who prematurely discontinue study drug prior to 48 weeks of treatment will have an EOT (W48D1) visit performed at the time of discontinuation followed by the Safety Follow-up visit within 28 days.

Patients must be discontinued from treatment for any of the following reasons:

- An AE that requires permanent discontinuation of study treatment
- Withdrawal of consent by the patient
- Treatment interruption for > 28 days due to a related AE
- Lack of efficacy
- Disease progression
- Pregnancy
- Patient lost to follow-up
- Investigator decision
- Noncompliance to protocol
- Termination of the study by the Sponsor

44 of 77

AEs leading to the discontinuation of study drug will be followed for 28 days after administration of last dose of study drug or until resolution, resolution to baseline, or until the event is considered stable or chronic.

7.2.2 Study Withdrawal

Patients may voluntarily withdraw from the study at any time for any reason without prejudice.

Patients may withdraw or be withdrawn from the study for any of the following reasons:

- Death
- Lost to follow-up
- Termination of study by Sponsor
- Withdrawal of consent

7.3 Lost to Follow-up

A patient will be considered lost to follow-up if he or she repeatedly fails to return for scheduled visits and is unable to be contacted by the study site.

The following actions must be taken if a patient fails to return to the clinic for a required study visit:

- The site must attempt to contact the patient and reschedule the missed visit as soon as possible and counsel the participant on the importance of maintaining the assigned visit schedule and ascertain whether or not the patient wishes to and/or should continue in the study.
- Before a patient is deemed lost to follow-up, the Investigator or designee must make every reasonable effort to regain contact with the patient with a minimum of 3 telephone contact attempts and if these fail, follow-up with a certified letter to the patient's last known mailing address These contact attempts should be documented in the patient's medical record.
- Should the patient continue to be unreachable, he/she will be considered to have withdrawn from the study.

8.0 STUDY ASSESSMENTS AND PROCEDURES

All study assessments will be performed at the visits and time points outlined in the Schedule of Events (Table 1-1, and Table 1-2).

8.1 Baseline Characteristics

8.1.1 Medical History

Medical histories will be obtained and will include demographic data; histories of acute, chronic, and infectious disease; surgical histories; and any reported conditions affecting major body systems. Any history of earlier chemotherapy or radiation therapy must be recorded.

All findings on medical history will be evaluated by the Investigator for clinical significance and patient's eligibility for trial participation.

8.1.2 MDS Disease History

Diagnosis of MDS with prior diagnostic cytogenetic and cytomorphologic evaluations, prior IPSS-R scores, and any prior therapies will be obtained.

8.1.3 Transfusion History

RBC transfusion history will be collected during Screening and will include up to a minimum of 16 weeks prior to initiation of study treatment on W1D1 (e.g., an RBC transfusion occurring prior to etavopivat dosing on W1D1 should be collected as part of the patient's transfusion history).

All transfusions, RBC and platelet transfusions received by the patients will be recorded in the source documentation and eCRF in a dedicated page, and not as medication history.

Sites who prescribe transfusions and have the transfusion records only in volumes should use for conversion of volume to units based on the following criteria, in order to obtain number of units within the last 16 weeks to assess the eligibility: one unit in this protocol refers to a quantity of packed RBCs approximately 200-350 mL. (i) Sites who use transfusion bags within this range, or ≥ 350 mL, the conversion in units should be done by dividing the volume transfused to the patient by 350 mL, (ii) sites who use transfusion bags < 200 mL, the conversion in units should be done by dividing the volume transfused to the patient by 200 mL.

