4.0 STUDY DESIGN

4.1 Overall Design

This study is a multicenter, open-label Phase 2 study in adult patients with very low, low risk or intermediate risk MDS per the IPSS-R classification (see Appendix B). The study will enroll approximately 45 patients (see Figure 3).

NTD – Not transfusion dependent; LTB – Low transfusion burden; HTB – High transfusion burden

- a. Patients who permanently discontinue treatment during the 48-weeks of treatment should complete both the End of Treatment visit (W48) and the Safety Follow-up visit (W52)
- b. Patients who demonstrate clinical benefit at 48 weeks of treatment, based on their MDS response assessment, may continue treatment in an optional Prolonged Treatment Period until the patient experiences unacceptable toxicities, disease progression, withdraws consent or meets any of the discontinuation criteria.
- c. After permanent discontinuation of treatment, study site may contact the patient approximately every 3 months for survival data.

Initially, 6 patients will be enrolled and dosed a minimum of 4-weeks with etavopivat 400 mg daily to confirm if safety, exposure, and pharmacological response (PK/PD profile) are consistent with prior experience of etavopivat dosing in healthy volunteers and patients with SCD or thalassemia.

Approximately 45 MDS patients (inclusive of the initial 6 patients enrolled for safety/PK/PD confirmation) will be enrolled and evaluated for an erythroid response based on the revised MDS IWG 2018 criteria (see Appendix A). Response assessment will be based on the individual patient's transfusion history in the 16 weeks prior to enrollment:

- NTD patients (received ≤ 2 RBC units for anemia within the prior 16 weeks): Hb increase of ≥ 1.5 g/dL over a continuous 8-week treatment period and no transfusion of RBC units for anemia over a continuous 8-week treatment period
 - o Approximately 15 NTD patients may be enrolled in this study
- LTB patients (received 3 to 7 RBC units within the prior 16 weeks): No transfusion of RBC units for anemia over a continuous 8-week treatment period
 - o Approximately 15 LTB patients may be enrolled in this study
- HTB patients (received ≥ 8 RBC units in the prior 16 weeks): $\geq 50\%$ reduction in RBC units transfused over a continuous 8-week period.
 - o Approximately 15 HTB patients may be enrolled in this study

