5.1 Inclusion Criteria

Participants are eligible to be included in the study only if all the following criteria apply:

Informed Consent

1. Patient has provided documented informed consent; the informed consent form (ICF) must be reviewed and signed by each patient prior to any study-related assessments/procedures being conducted.

Age

2. Age \geq 18 years at time of first dose

Sex and Contraceptive/Barrier Requirements

3. Patients, if female and of childbearing potential, must agree to use acceptable methods of contraception and agree not to donate ova from study start to 90 days after the last dose of study drug, and who if male are willing to use acceptable methods of contraception and agree not to donate sperm, from study start to 90 days after the last dose of study drug.

Disease Specific Requirements

- 4. Documented diagnosis of idiopathic/de novo MDS according to 2016 WHO classification (see Appendix C) that meets IPSS-R classification (see Appendix B) of very low, low, or intermediate risk disease, and:
 - < 5% blasts and no Auer rods in bone marrow based on local pathology review
 - < Intermediate risk cytogenetic abnormalities per IPSS-R
- 5. Anemia defined as:
 - NTD: Subjects with mean Hb concentration < 10.0 g/dL on 2 measurements (1 performed within 3 days prior to W1D1 and the other performed 7 to 28 days prior to W1D1, not influenced by RBC transfusion within 7 days of measurement) and < 3 RBC transfusions for anemia in the prior 16 weeks before W1D1 of etavopivat dosing

OR

- Transfusion Dependent: Subjects having received ≥ 3 units of RBCs for the treatment of anemia within 16 weeks prior to W1D1
- 6. Serum erythropoietin level > 200 U/L, OR, if \leq 200 U/L, subject is non-responsive, refractory, or intolerant to erythropoiesis-stimulating agents, or erythropoiesis-stimulating agents are contraindicated or unavailable.
- 7. Eastern Cooperative Oncology Group performance status of ≤ 2 (see Appendix D)

- 8. Subject is non-responsive, refractory, or intolerant to luspatercept, or luspatercept is contraindicated or not indicated.
- 9. No alternative treatment options are available and/or appropriate for the subject, at the discretion of the investigator.
- 10. Patient is willing and able to adhere to the study visit schedule and other protocol requirements

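### At volume-only sites, Protocol 8.1.3 counts an in-range RBC bag under 350 mL as less than one unit, which can move a patient near a cut-point into another stratum and HI-E criterion

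*Protocol*

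**What the plan says.** Protocol 8.1.3 gives a definition and then two conversion rules for sites that hold transfusion records only as volumes.

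- Definition: "one unit in this protocol refers to a quantity of packed RBCs approximately 200-350 mL".
- Rule (i), for bags inside that range and for bags of 350 mL or more: "the conversion in units should be done by dividing the volume transfused to the patient by 350 mL".
- Rule (ii), for bags under 200 mL: "the conversion in units should be done by dividing the volume transfused to the patient by 200 mL".
- Stated purpose: "in order to obtain number of units within the last 16 weeks to assess the eligibility".

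The 16-week count is used in two places. Protocol 5.1 opens the transfusion-dependent entry route to "Subjects having received ≥ 3 units of RBCs for the treatment of anemia within 16 weeks prior to W1D1". The NTD route asks for a mean Hb below 10.0 g/dL and "< 3 RBC transfusions for anemia in the prior 16 weeks before W1D1 of etavopivat dosing". Protocol 4.1, repeated in SAP 1.2.1, sets the strata on 16-week units: NTD at 2 or fewer, then "LTB patients (received 3 to 7 RBC units within the prior 16 weeks") and "HTB patients (received ≥ 8 RBC units in the prior 16 weeks").

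Under SAP 4.2.1.1 the Day 1 stratum determines the HI-E criterion. NTD patients need a sustained Hb rise of at least 1.5 g/dL without RBC transfusion. LTB patients need 8 weeks free of RBC transfusion. HTB patients need a cut of at least 50% in units over 8 weeks. Neither document gives a rounding rule for fractional units.

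**The concern.** The definition and rule (i) cannot both hold. A bag of 200 to 350 mL is one unit by definition, but rule (i) credits it with a full unit only at 350 mL. The two rules also produce a step at 200 mL, where a slightly larger bag earns much less credit than a slightly smaller one.

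The cut-points are whole numbers of units, so under-counting can push a patient below one of them. At the lower cut-point the entry route is at stake. At the upper one it is the stratum, and with it the response criterion: a patient who would be HTB under the definition is judged as LTB, on complete freedom from transfusion and not on a 50% cut. The SAP still reports HI-E pooled and within each stratum for the abbreviated CSR, so stratum membership still affects the results.

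**Working it through.** The plan states no converted count, so there is no figure of its own to reproduce. The inputs are the definition and divisors (Protocol 8.1.3), the entry cut-off of 3 units (5.1) and the strata of up to 2, 3 to 7, and 8 or more (4.1). Bag volumes are assumptions, because the documents name none.

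**Credit per bag.** Units = bag volume / 350 for bags of 200 mL or more, and bag volume / 200 for smaller bags.

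- 199 mL: 199/200 = 0.995
- 200 mL: 200/350 = 0.571
- 250 mL: 250/350 = 0.714
- 300 mL: 300/350 = 0.857
- 350 mL: 350/350 = 1.000

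**Counts near the cut-points.** Units = bags × volume / 350.

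| Bag (mL) | 3 bags | 8 bags | Bags needed for 3 units | Bags needed for 8 units |
|---|---|---|---|---|
| 200 | 1.71 | 4.57 | 6 | 14 |
| 250 | 2.14 | 5.71 | 5 | 12 |
| 300 | 2.57 | 6.86 | 4 | 10 |
| 350 | 3.00 | 8.00 | 3 | 8 |

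With each in-range bag counted as one unit, as the definition reads, three bags are LTB and eight are HTB in every row.

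**Shifts that no rounding removes** (down, to nearest or up).

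- Upper cut-point, LTB and not HTB: 8 to 12 bags of 200 mL (4.57 to 6.86), 8 or 9 bags of 250 mL (5.71, 6.43), and 8 bags of 300 mL (6.86).
- Lower cut-point, below 3 units: three bags of 200 mL (1.71).

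**Shifts that depend on the unstated rounding.**

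- 200 mL: 4 or 5 bags (2.29, 2.86) and 13 bags (7.43)
- 250 mL: 3 or 4 bags (2.14, 2.86) and 10 or 11 bags (7.14, 7.86)
- 300 mL: 3 bags (2.57) and 9 bags (7.71)

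In terms of bag size, eight bags stay below 8 units if each is under about 328 mL when rounding to nearest (7.5 × 350/8) and up to about 306 mL when rounding up (7 × 350/8). For three bags and 3 units the limits are about 292 mL (2.5 × 350/3) and 233 mL (2 × 350/3). Rounding down, any bag under 350 mL shifts both.

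**When a response changes.** A patient who is transfusion-free for 8 weeks meets both the LTB and the HTB criterion, given some transfusion in the 8 baseline weeks. A patient who never achieves a 50% cut meets neither. Only one who achieves the cut without becoming transfusion-free is a responder as HTB and a non-responder as LTB.

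**Percent reduction.** If the same divisor applies at baseline and on treatment, it cancels. A fall from 6 to 3 bags of volume v gives 1 − (3v/350)/(6v/350) = 50.0% for any v.

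**The case against.** The strongest reply is that 350 mL is a deliberate standard. A volume record needs some divisor, 350 mL lies within the defined range, and a common divisor keeps sites comparable by volume. That would explain rule (i) taken alone. It does not explain why credit falls from 0.995 to 0.571 between 199 and 200 mL, and nothing in 8.1.3 describes such a standard. The word approximately in the definition does not help either, because the divisors are exact.

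Bags over 350 mL move the other way: a 400 mL bag counts 1.14, and seven of them reach 8.0 units. This is correct, but those bags lie outside the defined range, so counting them as more than one unit does not contradict the definition.

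The stated purpose of the conversion is eligibility. Its use for strata is an inference, though a close one, since the strata are cut on units over the same 16 weeks.

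Three stronger readings are tempting and are not supported.

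- A reader might infer that a patient with three 200 mL bags is shut out of the study. The count does fail the 3-unit route. Entry by the NTD route then depends on Hb and on whether the limit of fewer than 3 transfusions means units or episodes, which the protocol leaves open. Read as units, counts between 2 and 3 also satisfy that limit.
- A reader might infer that the HTB percent reduction is distorted because Protocol 8.2.2 repeats no conversion for on-study transfusions. No section directs that one patient's transfusions be counted in two ways, and SAP 4.2.1.1 uses units on both sides of its formula. The silence is missing detail.
- A reader might infer a bias of known size in the response rate. The documents do not say how many volume-only sites or affected patients there are, so no size can be given.

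It also stands that a protocol edit now cannot change screening decisions or strata already assigned, and that SAP 4.2.1.1 names no hypothesis test, so any shift would be in a descriptive rate.

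**Conclusion.** Protocol 8.1.3 contradicts itself. As written, an in-range bag counts between 0.57 and 1.00 unit, although the definition makes it one. This is a wrong rule, not a missing detail; the absent rounding convention and the silence on on-study counting are missing details beside it.

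For a patient near a cut-point the rule can change the assignment. Three 200 mL bags fall below the 3-unit entry route at 1.71 units. Eight bags of 200, 250 or 300 mL become LTB instead of HTB whatever the rounding.

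This rests on assumed bag sizes and on strata being assigned from the converted count. The effect is confined to volume-only sites with in-range bags under 350 mL, and it may be zero. It alters a response only where the patient meets one stratum's criterion and not the other's. The inconsistency itself is certain; its effect on the results cannot be judged from the documents. It should be corrected and disclosed, but it does not by itself undermine the primary analysis.

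**What to change.** In Protocol 8.1.3, reconcile the unit definition with the two divisors so that an in-range bag gets a consistent count with no step at 200 mL. Dividing by the site's own bag volume within the range is one option, at the price of volume comparability between sites. State one rounding convention, applied before strata are assigned. State in Protocol 8.2.2 and SAP 3.3 and 4.2.1.1 that baseline and on-treatment units use the same counting rule.

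Because the study ended early, keep the Day 1 strata for the primary analysis. In the CSR, state whether any volume-only site enrolled patients and how their units were counted. Where volumes or bag sizes exist, show HI-E with re-derived units and strata as a sensitivity analysis only.

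The cost is one CSR statement and one table that may be empty. Re-derivation depends on the data held: Protocol 9.6.2.3 plans summaries by unit and by volume, but 8.2.2 does not request volume and the SAP transfusion analysis uses units only. If no volume-only site enrolled a patient, the statement alone closes the point.

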8.1.4 Medication History

All medications (prescription and non-prescription, herbal medications/natural health products, cannabinoids, and investigational drugs) taken by the patients during the 30 days prior to Screening will be recorded in the source documentation and eCRF as medication history. Additionally, non-prescription medications should be avoided for 7 days prior to W1D1, and 14 days for St. John's wort as outlined in Section 6.7.1.

8.1.5 Viral Serology / Antigen Testing

Viral serology / antigen testing will be performed during Screening and will include: HIV, HepBsAg, HepBcAb, and Hepatitis C virus (HCV) by polymerase chain reaction.

8.1.6 Bone Marrow Aspirate

A bone marrow aspirate (BMA) will be performed during the Screening period to confirm eligibility and IPSS-R score, including cytogenetics, and cytomorphology. Local analysis will be used for study entry criteria and treatment initiation, and redacted result reports shared with sponsor for eligibility confirmation. BMA screening samples (and where indicated, with results from local analysis) will be sent to central laboratories for confirmation of study entry criteria and for exploratory studies. If the IPSS-R score cannot be verified, or it is determined the patient had $\geq 5\%$ blasts at study entry, the patient may be taken off treatment.

8.2 Efficacy Assessments

8.2.1 MDS Disease Assessment

The MDS Disease Assessment will be performed as described in Table 1-1 and Table 1-2. The disease assessment will use response criteria per Cheson et al. 2006 (Appendix A) and will include assessment of hematologic improvement (HI-E criteria, modified based on Platzbecker et al. 2019).

An assessment of hematologic improvement response only may be made when a bone marrow aspirate is not performed (for example Week 24 Day 1 of treatment).

8.2.2 Assessment of Transfusions

RBC, and platelet, transfusions will be recorded on an ongoing basis throughout the study as indicated in Table 1-1 and Table 1-2. For any RBC, and platelet, transfusions received during the study, collect Hb and platelet values prior to transfusion, the number of units transfused, and the dates of transfusion. If available, the Hb/hematocrit of the transfused unit should also be collected.

8.2.2.1 LTB/HTB Patient Transfusion Treatment Plan:

Each patient will have an individualized transfusion treatment plan in place prior to study treatment (see Appendix G). This treatment plan assumes a pre-transfusion Hb value is collected within 7 days of a scheduled transfusion. The decision on the RBC transfusion schedule and amount of RBC units to transfuse will be based on the following parameters:

- 1) A baseline pre-transfusion Hb threshold determined by the mean of all documented pretransfusion Hb values during the 16 weeks prior to start of study treatment.
- 2) During treatment, if the pre-transfusion Hb level is increased by ≥ 1 g/dL compared to the pre-transfusion Hb threshold for that patient, transfusion may be delayed by a minimum of 7 days and/or the number of units transfused may be reduced by 1 or more RBC units.

8.2.3 Hemoglobin Response and Clinical Measures of Hemolysis

Hemoglobin response and measures of hemolysis (reticulocytes, unconjugated bilirubin, and LDH) will be assessed.

8.2.4 Iron Chelation Therapy and Iron Profile

Iron chelation therapy will be recorded at Screening and on an ongoing basis throughout the study.

Iron profile, consisting of ferritin, iron and transferrin levels, will be measured during Screening, on W1D1 and throughout the study.

8.2.5 Patient-Reported Outcomes

Patient-reported outcomes (PROs) will be evaluated using the PROMIS fatigue scale and the QUALMS assessment.

The PROMIS is a patient-reported health outcome measurement system which can be used to evaluate quality of life in both children and adults. The PROMIS Fatigue 7a short form will be administered during scheduled clinic visits. The QUALMS is a validated MDS specific scale developed through input from MDS patients, their caregivers and providers.

The PROMIS and The QUALMS assessments will be performed throughout the study, as indicated in Table 1-1 and Table 1-2.

